3. BACKGROUND

a. Past Experimental and/or Clinical Findings

There is a large amount of literature showing how digital health interventions can lead to improved clinical outcomes. In the area of voice assistant for use in diabetes care management, studies have shown that interactive voice responses through voice recognition software have the potential to improve medication and lifestyle modification adherence in diabetes and improve clinical outcomes. For example, in a randomized control trial of adults with diabetes, patients who received automated, interactive phone-delivered management interventions had greater decreases in hemoglobin A1c compared to standard of care (BMC Public Health 12 (2012), 602). Another randomized crossover study reported on a smartphone application that can synthesize verbal descriptions of meals and accurately return the corresponding insulin bolus dose (J Diabetes 10 (2018), 600-608). A similar voice-activated device was identified in calculating insulin dosages in the visually impaired with diabetic retinopathy (2011 24th Canadian Conference on Electrical and Computer Engineering (CCECE), 2011, pp. 000904- 000907.)

Ultimately, no study has yet embarked on what this study looks to investigate; however, a review of key leading opinions from clinical, engineering, and data security experts have identified smart devices, voice assistants and the Internet of medical things (IoMT) as a key untapped area of potential for optimizing the home health care ecosystem to reduce diabetic complications, including diabetic foot ulcers (Journal of diabetes science and technology 12 (2018), 577-586).

b. Findings from Past Animal Experiments

N/A

4. DEVICES USED IN THE STUDY

a. Investigational Devices (Including Commercial Devices Used Off-Label)

Investigational Device 1	
Name:	Echo Dot
Description:	Voice assistant
Significant Risk?	Non-significant risk
Rationale for Non-Significant Risk	This is a non-significant risk device because it doesn't pose a serious risk to health, safety or welfare of the subject. Its use is not of substantial importance in diagnosing, curing or treating disease.

Investigational Device 2	
Name:	Insulin titration algorithm
Description:	Insulin titration protocol algorithm
Significant Risk?	Non-significant risk
Rationale for Non-Significant Risk	PCPs routinely provide patients with instructions on how to titrate their insulin at home. This algorithm helps patients implement these instructions (which is something they would otherwise be doing with no assistance). We do not believe that the software is more dangerous than standard of care, and is hopefully safer for a few reasons: 1) The provider will be able to set a limit to how much and how often the algorithm will increase the insulin dose. 2) The provider will be able to set a maximum insulin dose. 3) The default insulin titration protocol that we provide mirrors the 2020 consensus statement from AACE (American Association of Clinical Endocrinologists) and ACE (American College of Endocrinology) guidelines (https://pro.aace.com/pdfs/diabetes/algorithm-exec-summary.pdf), but is more conservative to have less tolerance for hypoglycemic events 4) In partnership with Endocrinologists and as Internists ourselves, we have a well thought out, professional guideline-based, conservative hypoglycemia protocol that reduces insulin dose and automatically turns off the titration algorithm if needed to account for various clinical situations where hypoglycemia may be present. The protocol is also designed to account for when providers may have erroneously started too high an insulin dose. Please see our hypoglycemia protocol attached in section 16 for details. 5.) There are multiple steps for confirmation when reporting data to ensure correct data acquisition, including reminders with every single check in that a "fasting blood sugar" is one where one has not had anything to eat in the 8 hours prior

b. IDE-Exempt Devices

N/A

5. DRUGS, BIOLOGICS, REAGENTS, OR CHEMICALS USED IN THE STUDY

N/A

6. PARTICIPANT POPULATION

a. Planned Enrollment

- (i) 50 participants
- (ii) 50 participants
- (iii) Patients at Stanford Internal Medicine Clinics with a diagnosis of Type 2 Diabetes who are clinically indicated to initiate or increase their long acting insulin.

b. Age, Gender, and Ethnic Background

The age range of this study is 18 years of age or older. There are no conditions on the gender or ethnicity of the participant. Male and female participants are going to be enrolled and we aspire to keep an appropriate demographic distribution.

c. Vulnerable Populations

No vulnerable populations will be targeted in this study.

d. Rationale for Exclusion of Certain Populations

Children will not be included in the study because the Internal Medicine team involved specialises in adult care.

e. Stanford Populations

N/A

f. Healthy Volunteers

None

g. Recruitment Details

Our team will recruit patients with type 2 diabetes who have been recently started on insulin (or who are having active adjustments to their insulin regimen). To identify patients that may be eligible for recruitment, our team will use Stanford's STARR cohort discovery tool and an Epic workbench report overseen by [name], the Stanford Population Health Medical Director, and [name], the Stanford Population Health Quality manager. We will use these tools to create a report of patients at Stanford Internal Medicine and Endocrinology clinics with type 2 diabetes and a recent hemoglobin A1c greater than 8%. Specifically, this is done through a cohort discovery of patients who have seen providers who practice at the Stanford primary care and Endocrinology clinic sites. In addition, we will also be identifying patients through advertisements through the Stanford Diabetes Research Core (<https://sdrc.stanford.edu/sdrc-research-cores/detc/home>). Specifically, the recruitment director with the core, [name], will be giving us access to a listserv of Stanford-affiliated patients who have requested to be contacted about diabetes-related clinical trial opportunities.

For potential participants identified through STARR or Epic workbench reports, our team will first contact the primary care providers and/or Endocrinologists of these patients (depending on which providers are managing or co-managing the patient's diabetes regimen). If the primary care providers and/or Endocrinologists agree that their patient might benefit from inclusion in our study, a member of the patient's care team will first contact the patient to notify them of the study and obtain approval for initiation of the research team's enrollment process. Upon approval, our research team will reach out to provide more information and conduct the informed consent process if the patient would like to participate.

For potential participants identified through [name] listserv, if these participants directly respond to our listserv advertisement, our research team will reply back to them directly. Our team will also contact their primary care providers and/or endocrinologists if the potential participant decides to enroll in the trial.

h. Eligibility Criteria

i. Inclusion Criteria

We will include patients who are 18 years of age or older with a diagnosis of Type 2 Diabetes with need for initiation or increase of a long-acting insulin regimen.

ii. Exclusion Criteria

We will exclude patients who:

- are 17 years of age or younger
- are on insulin pumps
- have impaired decision-making capacity
- do not speak English
- do not own a smartphone or have access to a WiFi network at home (due to the technological requirements of the device and application)

i. Screening Procedures

As stated above, our team will screen patients by creating a STARR report of patients at Stanford Internal Medicine clinics with type 2 diabetes and a recent hemoglobin A1c greater than 8%. Our team will then reach out to the primary care providers of these patients to identify patients who are candidates for starting long acting insulin, or who are already on long acting insulin but having active adjustments to their regimen.

j. Participation in Multiple Protocols

During the enrollment process, we will ask patients if they are involved in other studies. We don't anticipate there being conflicts but if there are co-enrollments we will look into complications.

k. Payments to Participants

Participants in the intervention arm will not be paid but they will be allowed to keep the Amazon Echo Dot after their involvement in the study concludes. At the conclusion of the study, participants in the control arm will also be given an Amazon Echo Dot for compensation.

l. Costs to Participants

None

m. Planned Duration of the Study

The probable duration of the entire study is 18 months.

- (i) One month
- (ii) Two months per participant
- (iii) Up to 15 months

7. RISKS

a. Potential Risks

i. Investigational devices

As stated earlier, instructions to patients to change their insulin dose will always strictly adhere to the physician-prescribed insulin protocol. However, if the patient inaccurately self-reports blood glucose data, dose adjustments based on this data can cause medical complications. To minimize the risk of this, the application will ask the patient to confirm

self-reported data, and when the instructed intervention is read back, the device will again summarize the patient's self-reported data and be clear that the intervention is based on the data provided by the patient and is as instructed by the patient's provider (e.g. "Based on your reported fasting blood sugar of 182 this morning, your doctor has instructed you to increase your insulin glargine to 17 units tonight up from 15 units yesterday."). Furthermore, all dose adjustments will be small, making them very unlikely to cause major adverse events such as hypoglycemia.

ii. Investigational drugs

None

iii. Commercially available drugs, biologics, reagents or chemicals

None

iv. Procedures

No investigational procedures will be performed.

v. Radioisotopes/radiation-producing machines

None

vi. Physical well-being

vii. Risks of participating in this study include the possibility of inaccurate self-reporting by participants leading to improper insulin dose adjustments. As stated above, our application will confirm all self-reported data prior to logging it by reading back reported values to patients and requiring verbal confirmation from the patient. Furthermore, all dose adjustments will be small (ranging from 2-4 units based on the participant's prescription). Such small dose adjustments to long-acting insulin are very unlikely to cause major adverse events such as hypoglycemia. Psychological well-being

No risk to psychological well-being. We hope that the intervention group psychologically benefits from increased engagement in their health. Furthermore, our application will provide patients with positive messages of encouragement.

viii. Economic well-being

No risk to economic well-being.

ix. Social well-being

No risk to social well-being.

x. Overall evaluation of risk

Low

b. International Research Risk Procedures

N/A

c. Procedures to Minimize Risk

As stated earlier, all prompts delivered by the application will be strictly based on the patient's physician's care plan.

d. Study Conclusion

The experiment will terminate after two months of data collection per patient.

e. Data Safety Monitoring Plan (DSMC)

i. Data and/or events subject to review

N/A

ii. Person(s) responsible for Data and Safety Monitoring

N/A

iii. Frequency of DSMB meetings

N/A

iv. Specific triggers or stopping rules

N/A

v. DSMB Reporting

N/A

vi. Will the Protocol Director be the only monitoring entity? (Y/N)

Yes

8. BENEFITS

PHI will only be collected once during enrollment, which includes an entry survey on REDCap (screenshots attached). The least amount of information will be obtained to accomplish the purpose of the research. This data will be stored securely in a folder on the HIPAA-compliant Stanford Medicine Box. A unique study ID will be randomly generated for each patient (not derived from any identifiable information). This ID will be used with our application and will be linked with the self-reported patient data that we collect using the Amazon Echo Dot. No PHI will be collected or stored by our application on the Amazon Echo Dot.

9. PRIVACY AND CONFIDENTIALITY

All participant information and specimens are handled in compliance with the Health Insurance Portability and Accountability Act (HIPAA) and privacy policies of Stanford University, Stanford Health Care, and Stanford Children's Health.

Using an AI-based Voice Assistant to Manage Insulin in Diabetes: a Randomized-Control Trial

NCT05081011

February 2, 2021

Power and sample size calculation

Sample size was determined to be 32 participants for 80% power and a 2-sided alpha of 0.05 to detect a treatment difference of 84% for the voice AI group vs 40% for the standard of care group for the proportion that achieve glycemic control. We decided to use our secondary outcome of glycemic control as the basis of our power calculation because it has been used in prior studies.

The treatment difference of 84% vs 40% was based on a similar study which found a 2:1 (60% vs 30%) treatment difference for their digital intervention. Given that this similar study supported titration of more complicated insulin regimens and did not utilize voice, we felt that an increased projected treatment effect of 84% for our intervention was reasonable. We also requested and received approval to recruit up to 50 participants to account for drop out.

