Recruitment process: When an eligible candidate is identified per the screening process above, the research team will contact the patient's primary care physician and inform them of this study. If the patient's primary care physician agrees that the patient would benefit from inclusion in this study, they will reach out to the patient and describe the trial to them. If the patient agrees to be contacted by the research team, their care team member will share their information with a member of the research team via secure message and a member of the team will reach out via the participant's preferred method of communication (phone, email, etc). Due to the COVID- 19 pandemic and the fact that diabetes is a risk factor for the virus, all participants will undergo the informed consent process remotely. The research team will make contact with the participant via the mechanism shared with them by the treating team, introduce the project and ask if the participant would like to undergo the informed consent process via an online REDCap survey (screenshots attached) or via a paper consent form sent in the mail. The research team member will then send the Informed Consent Form (ICF) to the participant via either a URL by email or a paper ICF by mail. The research team member will set up a time to discuss the ICF with the participant either by phone or video chat and will describe the study to the participant, review the risks and benefits outlined in the study consent form and address any questions from the participant before asking them for their consent to participate in the study. After consent is obtained, participants will complete an intake survey ("Participant Information Survey") and will be randomized to either the intervention or control group. All participant information obtained during enrollment will be stored securely in a HIPAA-compliant and PHIsafe Stanford Medicine Box folder.

Device setup:

After consent is obtained, the participant's treating physician will communicate their desired insulin protocol with the research team. The information communicated will include the following:

- Starting insulin prescription
- Goal fasting blood sugar
- Titration parameters (e.g. Increase starting dose by 2 units every 3 days if not at goal fasting blood sugar)
- Situations in which they would want their patient to contact their provider or seek immediate medical attention and call 911/report to an ER.

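### With 32 evaluable participants, 80% power and a two-sided 5% error rate cannot both hold for 84% vs 40%, and the SAP names neither the test nor the allocation ratio

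*SAP*

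**What the plan says.** The SAP's section on power and sample size reads: "Sample size was determined to be 32 participants for 80% power and a 2-sided alpha of 0.05" and continues "to detect a treatment difference of 84% for the voice AI group vs 40% for the standard of care group", the outcome being the proportion achieving glycemic control. It explains the choice of outcome: "We decided to use our secondary outcome of glycemic control as the basis of our power calculation". On attrition it says: "We also requested and received approval to recruit up to 50 participants to account for drop out". It gives no dropout rate, formula, software, test or allocation ratio.

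The protocol does not fill these gaps. Section 2a (recruitment process) says only that participants "will be randomized to either the intervention or control group". The data analysis text in section 2a is descriptive and names no test. Section 6a gives planned enrolment as "i) 50 participants". Because 50 is the number recruited to allow for dropout, 32 is read here as the number evaluable.

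**The concern.** A power statement makes a joint promise: the stated chance of detecting the effect, at the stated error rate. With 16 per arm and one rate as high as 84%, large-sample formulas are unreliable, and different standard formulas give totals from 32 to 46. The SAP gives the lowest of these and does not say which test the result belongs to.

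Two things are at stake. First, readers will take 80% power and 5% error as holding together at 32 evaluable. Second, they will take the gap between 32 and 50 as the loss the trial can absorb. If 32 is too few, that allowance is too generous. This is also the only power calculation in the documents, so it is the only quantitative support for the sample size.

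**Working it through.** **Inputs.** From the SAP: 84% and 40%, two-sided alpha 0.05, power 80%, total 32, recruitment up to 50. Assumed, because the documents are silent: 1:1 allocation (other splits are checked below) and an unadjusted comparison of two proportions.

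**1. Reproducing 32.** The unpooled formula at 1:1 gives, per arm,

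(1.960 + 0.842)² × (0.84×0.16 + 0.40×0.60) / 0.44² = 15.18, so 16 per arm and 32 in total.

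The nominal power at 16 per arm is 82.0%. That the sponsor used this formula is an inference. At 1:2 (voice AI to standard of care) the same formula gives 10.31 and 20.63, so 11 + 21, which is also 32. Other common 1:1 formulas give more:

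| Formula | Per arm | Total |
|---|---|---|
| Unpooled | 15.18 → 16 | 32 |
| Pooled | 17.88 → 18 | 36 |
| Arcsine (h = 0.949) | 17.43 → 18 | 36 |
| Continuity-corrected | 22.19 → 23 | 46 |

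**2. Exact power and size.** All possible 2×2 tables were enumerated with binomial probabilities. Power was taken at 84% vs 40%. Size is the largest two-sided error over 1,999 values of a common rate.

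| Test | Power, 16:16 | Maximum size, 16:16 | Power, 25:25 |
|---|---|---|---|
| Unpooled Wald | 80.5% | 7.2% | 93.4% |
| Pearson chi-square | 77.1% | 5.8% | 92.9% |
| Barnard | 73.8% | 4.5% | 91.4% |
| Boschloo | 73.0% | 4.1% | 91.4% |
| Fisher | 61.6% | 2.0% | 87.4% |

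Fisher at exactly 16:16 is a low point: it has 68.2% at 17:15 and 71.2% at 15:17. At 16:16 none of the five tests has both 80% power and size within 5%.

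**3. A ceiling that does not depend on the list of tests.** With equal arms and a common rate, swapping the arms leaves the distribution of the data unchanged. A test that treats the arms alike and holds 0.05 two-sided therefore has at most 0.025 in each direction. The most powerful one-sided 0.025 test of a common rate of 0.651 against 84% vs 40% has 76.2% power at 16:16. A linear program over all rejection rules, randomized ones included, with size at most 0.025 at every common rate gives the same 76.2%.

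**4. Unequal splits of 32.** Holding 0.025 per direction, the ceiling is 71.1% to 76.4% for splits from 11:21 to 21:11. It is highest at 17:15, and no split from 8:24 to 24:8 exceeds 76.4%. Barnard and Boschloo at two-sided 0.05, without forcing equal tails, give 69.6% to 75.9% for splits from 11:21 to 21:11. At 18:18 the ceiling rises to 81.1%.

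**5. Dropout.** If 50 are randomized 25:25 and 32 remain after loss at random, average power over the resulting splits is Wald 79.4%, Pearson 76.3%, Boschloo 73.9%, Barnard 72.8% and Fisher 66.9%.

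The total at which 80% is reached depends on how it is judged:

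- *On average over random splits from 25:25:* Pearson has 82.1% at 36. Barnard and Boschloo have 79.7% and 79.6% at 36, then 80.4% and 80.5% at 37. Fisher has 80.0% at 41 and 80.8% at 42.
- *At every split with at most 25 per arm and arms differing by at most 8:* from 39 up for Barnard (lowest 81.0%) and Boschloo (lowest 80.4%), and from 43 up for Fisher (lowest 80.2%, at 22:22). Below these totals some splits fail: Barnard and Boschloo have 79.0% at 19:17, and Fisher has 77.1% at 21:21.

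As loss from 50: 32 is 18/50 = 36%, 39 is 11/50 = 22%, and 43 is 7/50 = 14%.

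**The case against.** The strongest reply is that 32 is not an arithmetic slip. It follows from a standard approximation, large-sample sizing is ordinary practice, and the matching Wald test does have 80.5% exact power. The SAP does not promise exact error control at every common rate, and with Pearson's test the shortfall is only about 3 points. All of that is true. What remains is that the Wald test reaches 80% only with an error rate of up to 7.2%, so the statement fails on alpha instead of on power. The ceiling of 76.2% shows that a different choice of unadjusted test at 16 per arm would not rescue it. A covariate-adjusted analysis lies outside that ceiling, but the documents plan none.

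A second reply is that the documents never say 36% loss is tolerable. That is also true: the figure is only what 32 of 50 implies. The totals of 39 and 43 are conservative, because they cover uneven splits such as 16:23 and 25:18. On average over random loss, 80% is reached a little earlier, from about 37 and 41. On either basis, 32 is too few.

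Third, the outcome is secondary, feasibility is a stated purpose of the study, and full enrolment gives at least 87%. This stands, and it limits how serious the point is.

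**Conclusion.** The concern holds. The stated power and the stated alpha do not hold together at 32 evaluable participants for 84% vs 40%. Realistic power at 16 per arm is 73% to 77% with Boschloo, Barnard or Pearson (Pearson slightly exceeding 5% error) and 61.6% with Fisher, under a ceiling of 76.2% for any unadjusted test that holds 0.025 per direction. The missing allocation ratio does not change this, since no split of 32 that was checked has a higher ceiling than 76.4%.

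The conclusion takes the SAP's response rates as given, reads 32 as the evaluable number, and assumes an unadjusted comparison. It should be fixed but is moderate in weight: the outcome is secondary, and at 25:25 power is between 87.4% and 93.4% with every test checked.

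**What to change.** In the SAP, state the allocation ratio, name the test for glycemic control, and restate the power to match. For 1:1, for example: *With 1:1 allocation and 84% vs 40%, 32 evaluable participants (16 per arm) give about 74% power with Barnard's test, or 73% with Boschloo's test, at two-sided 0.05; 50 evaluable (25 per arm) give about 91% with either.* If Pearson's chi-square is chosen, state 77% at 16 per arm together with its exact size of up to 5.8%.

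Do not quote a single minimum evaluable number or tolerable loss worked out from equal arms. Exact power is saw-toothed in the sample size, and dropout may leave the arms unequal. As a conservative guide for arms differing by no more than 8, 80% is reached from about 39 evaluable with Barnard or Boschloo and about 43 with Fisher. Recompute for the actual ratio and split.

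The cost is SAP wording only, and approved enrolment of up to 50 is unchanged. The price is a lower stated power at 32 and, on the conservative guide, an implied dropout allowance of about 22% (Barnard or Boschloo) or 14% (Fisher) instead of 36%.
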